## Fold Increase

The fold increase is defined as a subject's post Baseline titer at Visit X, divided by the baseline titer. Main study fold increase is defined based on the main baseline. Booster sub-study fold increase can be defined based on the booster baseline or the main baseline.

## 1 Introduction

This Statistical Analysis Plan (SAP) details the statistical methodology to be used in analyzing study data and outlines the key statistical programming specifications for the booster sub-study of clinical trial RSV-MVA-002. It describes the variables and populations, anticipated data transformations and manipulations, and other details of the analyses not provided in the study protocol. The SAP is written based on recommendations from *ICH E3: Structure and Content of Clinical Study Reports*, and *ICH E9: Statistical Principles for Clinical Trials*. Table, figure and listing shells are described in a separate document.

The analyses described here are based on the final clinical trial protocol RSV-MVA-002 Edition 4.0 dated April 26, 2018. Details for the analyses of the main study data are described in the final SAP dated May 31, 2017 and the SAP Addendum dated October 11, 2017. This plan covers analysis details of data collected for the booster sub-study. It will be followed completely for the analysis of data derived from the sub-study. If any unforeseen additional analyses are included in the clinical study report (CSR) they will be clearly described as additional, unplanned analyses.

## 2 Trial Overview

### 2.1 Trial Description

This is a randomized, single-blind, placebo-controlled, dose-ranging Phase II trial in  $\geq 55$  year old adults to evaluate the safety and immunogenicity of the recombinant MVA-BN-RSV vaccine. A total of 420 subjects were recruited into five treatment groups and were vaccinated in the main study (see Table 2).

**Table 2 Treatment Groups in the Main Study**

| Group        | N          | Age [years] | Volume per dose [mL] | 1 st vaccination
Day 0
[Inf.U] | 2 nd vaccination
Day 28
[Inf.U] | Route |
|--------------|------------|-------------|----------------------|---|--|-------|
| 1     | 78         | $\geq 55$   | 0.5                  | $1 \times 10^8$                                 | Placebo  | IM    |
| 2     | 89         | $\geq 55$   | 0.5                  | $1 \times 10^8$                                 | $1 \times 10^8$                                  | IM    |
| 3     | 80         | $\geq 55$   | 0.5                  | $5 \times 10^8$                                 | Placebo  | IM    |
| 4     | 90         | $\geq 55$   | 0.5                  | $5 \times 10^8$                                 | $5 \times 10^8$                                  | IM    |
| 5     | 83         | $\geq 55$   | 0.5                  | Placebo   | Placebo  | IM    |
| Total | 420 |             |                      |   |  |       |

Approximately one year after their first vaccination in the main study, 86 subjects in two selected treatment groups of the main study (Group 1 and Group 3) are planned to be recruited to participate in the booster sub-study. They will receive a single booster vaccination using the same MVA-BN-RSV dose they received during the main study. Subjects will be followed up for 12 months after their booster vaccination. Out of these 86 subjects, approximately 26 will be recruited from the PBMC subgroup (approximately 13 subjects for each of the two selected dose

---

groups). The selection of the treatment groups to be included in the booster sub-study is based on the results of the main study.

## **2.2 Design Techniques to Avoid Bias**

Eligible subjects who have consented to participate in the booster sub-study will be enrolled until a total of 86 is reached. PBMC sites will begin recruitment 1-2 weeks prior to the remaining sites to ensure 13 PBMC subjects per treatment group. Once 46 subjects are enrolled into one treatment group, enrolment for that group will stop to assure an approximately equal number of enrolled subjects in both treatment groups.

### **2.2.1 Methods of Assigning Subjects to Treatment Groups**

Subjects in this booster sub-study will not be randomized. They will get the same dose received during the main study.

### **2.2.2 Blinding**

Subjects in the booster sub-study will not be blinded because they will get the same dose received in the main study, which has already been unblinded.

## **2.3 Objectives**

### **2.3.1 Primary Objective**

The primary objective of the main study is to assess the optimal dose and schedule of the MVA-BN-RSV vaccine in adult and elderly subjects in terms of immunogenicity.

The objective of the booster sub-study is to demonstrate that the immune response of subjects previously vaccinated with MVA-BN-RSV vaccine can be boosted one year later with a single MVA-BN-RSV vaccination.

### **2.3.2 Secondary Objectives**

The secondary objectives of the main study are:

- To assess safety and reactogenicity of the MVA-BN-RSV vaccine in adult/elderly subjects
- To assess the RSV-specific humoral immune responses (in all subjects) and cellular immune responses (in a subgroup population of each group) against the MVA-BN-RSV vaccine in adult/elderly subjects.
- To explore a potential correlation of the RSV-specific immune response to RSV related respiratory disease symptoms.

---

The secondary objectives of the booster sub-study are:

- To assess the RSV-specific immune responses elicited by the MVA-BN-RSV vaccine (in subjects of the selected treatment groups) one year after the last vaccination in the main trial in adult/elderly subjects.
- To assess the RSV-specific humoral immune responses (in subjects of the selected treatment groups) and cellular immune responses (in the respective subgroup population of the selected treatment groups) of the MVA-BN-RSV vaccine following a one year booster vaccination in adult/elderly subjects.
- To identify further potential differences in durability and/or boostability of immune responses in the two chosen MVA-BN-RSV dose regimens.
- To assess safety and reactogenicity of the MVA-BN-RSV vaccine following the booster vaccination in adult/elderly subjects

## 2.4 Study Population

In the main study, subjects were stratified by age into two groups:  $\geq 55$  to  $< 70$ , and  $\geq 70$  years. At least 20 subjects per treatment group were required in the age stratum  $\geq 70$  years.

The booster sub-study will enroll approximately 43 subjects from each of the two selected dose groups regardless of age subgroups.

## 2.5 Inclusion Exclusion Criteria

Subjects who completed all vaccinations of the main trial according to protocol in the selected dose groups and signed the booster sub-study informed consent are eligible to participate in the booster sub-study. A list of exclusion criteria for the booster sub-study is provided in the study protocol. Subjects are required to meet none of the exclusion criteria to enter the sub-study.

## 2.6 Endpoints

Primary and secondary endpoints for the main study are provided in the study protocol and in the main study SAP and SAP Addendum. Endpoints described in this section are relevant to the booster sub-study only.

### 2.6.1 Immunogenicity Endpoints

The immunogenicity endpoints for the booster sub-study are:

- RSV-specific antibody response rate measured by Immunoglobulin G (IgG) Enzyme-linked Immunosorbent Assay (ELISA) (total RSV, G protein A strain, G protein B strain) at all post booster vaccination immunogenicity serum sampling time points and based on the individual peak titers.

- RSV-specific GMT measured by IgG ELISA at all immunogenicity serum booster sampling time points and based on the individual peak titers.
- RSV-specific antibody response rate measured by Immunoglobulin A (IgA) ELISA at all post booster vaccination immunogenicity serum sampling time points and based on the individual peak titers.
- RSV-specific GMT measured by IgA ELISA at all immunogenicity serum booster sampling time points and based on the individual peak titers.
- RSV-specific antibody response rate measured by PRNT (RSV strain A) at all post booster vaccination immunogenicity serum sampling time points and based on the individual peak titers.
- RSV-specific GMT measured by PRNT (RSV strain A) at all immunogenicity serum booster sampling time points and based on the individual peak titers
- RSV-specific antibody response rate measured by PRNT (RSV strain B) at all post booster vaccination immunogenicity serum sampling time points and based on the individual peak titers.
- RSV-specific GMT measured by PRNT (RSV strain B) at all immunogenicity serum booster sampling time points and based on the individual peak titers.
- RSV-specific antibody response rate measured by IgA ELISA at all post booster vaccination nasal swab sampling time points (mucosal IgA) and based on the individual peak titers.
- RSV-specific GMT measured by IgA ELISA at all nasal swab booster sampling time points (mucosal IgA) and based on the individual peak titers.
- RSV-specific response and responder rates measured by Interferon gamma (IFN- $\gamma$ ) and Interleukin 4 (IL-4) Enzyme linked Immuno Spot Technique (ELISPOT) at all post booster vaccination PBMC sampling time points until BEAP.
- RSV-specific median and geometric mean Spot Forming Units (SFU) measured by IFN- $\gamma$  / IL-4 ELISPOT at all PBMC booster sampling time points until BEAP.
- RSV-specific memory B cells measured at Booster Follow Up Visit 1 (BFU1) and Booster Follow Up Visit 2 (BFU2).

## 2.6.2 Safety Endpoints

The safety endpoints are:

- Occurrence, relationship to the trial vaccine and intensity of any serious adverse event (SAE).
- Occurrence of any Grade 3 or higher adverse events (AE) possibly, probably or definitely related to the trial vaccine within 4 weeks after the booster vaccination.
- Occurrence, intensity and duration of solicited local AEs during the 8-day period (day of vaccination and the following 7 days) after the booster vaccination.

---

- Occurrence, relationship to the trial vaccine, intensity and duration of solicited general AEs during the 8-day period (day of vaccination and the following 7 days) after the booster vaccination.
- Occurrence, relationship to the trial vaccine and intensity of unsolicited non-serious AEs within 4 weeks after the booster vaccination.

## 2.7 Interim Analysis

An interim topline analysis is planned when all subjects enrolled in the booster sub-study have completed the BFU1 visit. Refer to Appendix [6.3](#) for the tables that will be provided for the interim topline analysis.

## 3 Study Design

Refer to the schedule of events in Appendix [6.2](#).

## 4 Statistical Methods

### 4.1 Planned Sample Size

From two treatment groups selected based on immunogenicity/safety parameters following primary vaccination, approximately 43 subjects will be recruited into the booster sub-study (86 subjects in total). Out of these 86 subjects, approximately 26 subjects (13 subjects for each dose group) will be recruited from the PBMC subgroup.

Based on the variability observed in the  $\log_{10}$  titers for PRNT (A strain) 2 weeks after the second vaccination in the main study, the standard deviation (SD) is estimated to be 0.335 for the  $\log_{10}$  titers 2 weeks after the booster vaccination. A total of 40 evaluable subjects per group will provide 80% power to detect a difference of 0.213 ( $\log_{10}$ -scale) at a significance level of 5% (two-sided), which corresponds to a ratio of 1.63 in GMTs. Considering a drop-out rate of 5%, 43 subjects per group will be enrolled to receive a booster vaccination.

The sample size for the main study has been initially estimated based on the need to detect a significant difference between the two doses to select the optimal dose for further development. However, only a descriptive comparison is planned between the two dose groups in the sub-study.

The primary objective of the booster sub-study is to demonstrate that the immune response of subjects previously vaccinated with MVA-BN-RSV vaccine can be boosted one year later with a single MVA-BN-RSV vaccination. When the sample size is 40, a paired t-test with a 0.025 one-sided significance level will have >80% power to reject the null hypothesis that the difference in immune response ( $\log_{10}$  titers) after the initial vaccination and that after the booster vaccination is 0.08 or farther from zero when the expected difference is 0, assuming that the standard deviation of the differences is 0.168 ( $\log_{10}$ -scale). This comparison is also considered descriptive.

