**Table 11 Serum RSV-Specific Baseline and Individual Peak Geometric Mean Titers – FAS and PPS**

	Analysis group							
	Adult low (N=18 b )		Adult standard (N=18)		Elderly standard (N=18)		Placebo a (N=9)	
Week (Visit)	GMT	95% CI	GMT	95% CI	GMT	95% CI	GMT	95% CI
Serum RSV-specific IgG ELISA GMT								
Week 0 (V1)	1146	915, 1437	1121	830, 1512	913	726, 1149	1005	710, 1422
Individual Peak GMT	1807	1435, 2276	2238	1622, 3089	2286	1725, 3030	1289	913, 1820
Serum RSV-specific PRNT (strain A) GMT								
Week 0 (V1)	546	380, 783	652	474, 897	625	456, 857	524	374, 734
Individual Peak GMT	926	676, 1268	1394	1087, 1788	944	677, 1315	782	560, 1093
Serum RSV-specific PRNT (strain B) GMT								
Week 0 (V1)	256	173, 379	327	190, 561	242	154, 380	231	116, 456
Individual Peak GMT	379	245, 587	512	322, 814	374	231, 604	347	189, 636
CI = confidence interval; ELISA = enzyme-linked immunosorbent assay; FAS = full analysis set; GMT = geometric mean titers; IgG = immunoglobulin G; PPS = per protocol set; RSV = respiratory syncytial virus								
a Adult and elderly placebo combined.								
b Only 17 of 18 subjects had available data in this group at Week 8 (V7).								
Source: MVA-RSV-001 Clinical Study Report (Ed. 1), Tables 15.2.2.5, 15.2.4.5 and 15.2.5.5.								

The cellular immune response was assessed using an IFN- $\gamma$ /IL-4 ELISPOT assay using three different RSV peptide pools (F, G and N) as well as RSV for stimulation. IFN- $\gamma$  secreting T cells specific for the F, G and N protein increased in all active treatment groups, with no substantial differences between vaccine dose and age whereas numbers of IL-4 producing T cells were low or below the detection limit. No dose dependency was seen in terms of Geometric Mean Spot Forming Units (GMSFUs). The T cell response boosted by the normal dose in the adult and elderly group was comparable. The responder rate based on IFN- $\gamma$  producing PBMCs was highest in the elderly standard dose group, ranging from 66.7% (12/18) to 94.4% (17/18) of subjects for all stimulating agents. Responder rates based on IFN- $\gamma$  and IL-4 producing PBMCs are summarized in [Table 12](#).

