##### **PRNT (A strain) titers**

The primary analysis of the endpoint is Geometric Mean Titers (GMTs) after a single booster MVA-BN-RSV vaccination measured by Plaque Reduction Neutralization Test (PRNT; against strain A) 2 weeks post vaccination.

PRNT (A strain) titers will also be summarized descriptively using the geometric mean of fold increase, positivity rates (including associated 95% CI's), and response rates (including associated 95% CI's) for each treatment group, and by age group at each sampling point. In order to compare immune responses after initial vaccination in the main study and after booster vaccination in the booster sub-study, the summary will include data from all sampling points in the main study as well as those in the booster sub-study for the BFAS. Fold increase and response rates in the main study visits will be based on the main baseline; fold increase and

---

response rates in the booster visits will be based on the booster baseline. In addition, fold increase for post booster baseline time points will also be summarized based on main baseline.

Descriptive comparison of the ratios of the GMTs and GMFI's between the two treatment groups (Group 3 / Group 1) by visit will be calculated along with the corresponding 95% CI by assuming that the log10 PRNT (A strain) titers and log10 PRNT (A strain) Fold Increases are normally distributed:

Pair differences in log10 titer (main study log10 titer - booster sub-study log10 titer) and fold increase from booster sub-study at similar post-vaccination time points will be calculated, as well as their 95% CI. This will be presented as ratio and the corresponding 95% CI in the original scale. Fold increase in the main study visits will be based on the main baseline; fold increase in the booster visits will be based on the booster baseline.

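### The >80% power stated for the booster's paired titer comparison rests on an unsourced SD of differences (0.168) that, with the SAP's own titer SD, needs titers a year apart to correlate at about 0.86 or more; its null also has no direction

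*SAP*

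**What the plan says.** Booster SAP section 4.1 makes two power statements.

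- **Between groups.** From main-study variability two weeks after the second vaccination, "the standard deviation (SD) is estimated to be 0.335" for log10 PRNT A titers two weeks after the booster. On that basis "A total of 40 evaluable subjects per group will provide 80% power" for a difference of 0.213 log10. Protocol section 9.2 carries the same calculation.
- **Within subjects.** For what 4.1 calls the primary objective of the sub-study: "When the sample size is 40", "a paired t-test with a 0.025 one-sided significance level will have >80% power" to reject a difference between the post-primary and post-booster responses of "0.08 or farther from zero when the expected difference is 0", "assuming that the standard deviation of the differences is 0.168" on the log10 scale. This comparison is then described as descriptive. Protocol 9.2 has no counterpart.

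The analysis is in 4.5.7 (PRNT A strain titers): paired differences, main study minus booster, "at similar post-vaccination time points will be calculated, as well as their 95% CI", shown as a ratio. Table 15.2.1.8 reports it and is marked for the topline readout.

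**The concern.** The SD of 0.335 is tied to observed data. The SD of 0.168 is not tied to anything: 4.1 gives no source, and no within-subject SD or correlation appears in the protocol or either SAP. It equals half of 0.335 after rounding (0.1675). The documents do not say that it was obtained by halving, and the point does not depend on that. Whatever its origin, it carries an unstated requirement on the correlation between two titers that follow separate vaccinations 11 to 13 months apart (booster schedule, footnote 11), in a population where the protocol (section 2.1) calls RSV re-infection common at all ages.

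The stake is interpretation. A reader told that the comparison had >80% power may take a confidence interval that fails to exclude a 0.08 log10 shortfall (10^0.08 = 1.20-fold) as a sign of a weaker booster response. If the SD of differences is larger than assumed, such intervals would be common even with no true difference.

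**Working it through.** **Inputs** (all booster SAP 4.1): n = 40 pairs; margin 0.08 log10; true difference 0; one-sided alpha 0.025; SD of differences 0.168; SD of a single titer 0.335.

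**1. The plan's figure, one-direction null.** Noncentrality = 0.08 / (0.168/√40) = 3.01, df 39. Noncentral t power = 83.6% (normal approximation 85.4%). The >80% claim reproduces. So does the neighbouring between-group figure: 40 per group, SD 0.335, difference 0.213 gives 80.2%, and 10^0.213 = 1.63.

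**2. Correlation implied by 0.168.** With a common SD s, SD_diff = s·√(2(1 − ρ)), so ρ = 1 − SD_diff²/(2s²). With s = 0.335: 1 − 0.168²/(2 × 0.335²) = 0.874.

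**3. Break-even for 80% power.** The largest SD of differences that gives 80% at n = 40 is 0.1761. Then ρ = 1 − 0.1761²/(2 × 0.335²) = 0.862.

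**4. Sensitivity to the titer SD.**
- If only the booster-visit SD is held at 0.335 and the earlier SD may take any value, the smallest correlation that works is √(1 − 0.1761²/0.335²) = 0.851.
- If the common SD were 0.25: 1 − 0.1761²/(2 × 0.25²) = 0.752.
- If it were 0.275: 1 − 0.1761²/(2 × 0.275²) = 0.795.
- If it were 0.40: 0.903.

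**5. Power and excludable ratio by correlation** (s = 0.335, n = 40). The margin excluded with 80% power is SD_diff × 0.08/0.1761; the ratio is 10 to that power.

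| ρ | SD of differences | Power at margin 0.08 | Ratio excluded with 80% power |
|---|---|---|---|
| 0.875 | 0.168 | 84% | 1.19 |
| 0.80 | 0.212 | 64% | 1.25 |
| 0.70 | 0.259 | 48% | 1.31 |
| 0.50 | 0.335 | 31% | 1.42 |

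**6. The null as written.** A null of 0.08 or more from zero, with no direction, is literally a two-sided equivalence null. Rejecting it needs both one-sided tests at 0.025 to succeed. At SD 0.168 and true difference 0, simulation (400,000 runs) gives about 67%; the check 2 × 0.836 − 1 = 0.67 agrees. Reaching 80% on this reading would need an SD of differences of about 0.152, that is ρ of about 0.90. So the stated power fits only a one-direction null that the text does not state.

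**The case against.** The strongest reply is that this is an unsourced planning assumption with little riding on it, and much of that stands. The arithmetic is right on the stated inputs. The 43 per group come from the between-group calculation. Section 4.5.7 sets no margin, test or success rule for the paired comparison, and the reported 95% CI will show the precision actually achieved whatever SD was assumed. Fold increase and response rates against booster baseline, which do not use 0.168, also bear on whether the response can be boosted.

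It is also fair that 0.335 need not apply at both visits. It was observed after a second vaccination, whereas Groups 1 and 3 had one active dose. The PRNT A intervals for the vaccinated groups in protocol Table 11 (n = 18, t-based limits) imply SDs of roughly 0.22 to 0.32, and a common SD in that range lowers the required correlation (step 4). If the two groups were pooled (80 pairs), the break-even would fall to about 0.72, but 4.1 states 40.

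What does not fall away: 4.1 attaches a numerical power claim to the sub-study's stated objective, the claim depends on a quantity without support, and the null as worded does not match it.

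A reader might go further and infer from Table 11 that 0.168 is too small, because the placebo group's "Serum RSV-specific PRNT (strain A) GMT" rose from 524 at baseline to 782 at peak without vaccine. The documents do not support that. There are nine subjects; their intervals imply a total between-subject SD of only about 0.19, which sits badly with a large within-subject SD; and sampling error in the rise, the number of repeat titers and natural exposure would all have to be assumed. Protocol 2.6 itself calls these data exploratory.

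**Conclusion.** The point holds as one of unsupported assumption and mismatched wording, not of miscalculation. On the SAP's own SD of 0.335 at both visits, the >80% claim requires a within-subject correlation of about 0.86 or more (at least 0.85 with only the booster-visit SD fixed; about 0.75 to 0.80 if the common SD were 0.25 to 0.275). No passage supports any of these. Separately, and independently of any correlation, the null as written gives about 67% power on the SAP's own inputs.

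Two stronger readings are not supported. One is that the comparison is in fact underpowered: the true SD of differences is not in the documents, and if it is 0.176 or less the one-direction claim stands. The other is that the authors halved the cross-sectional SD: the numerical match is exact to rounding, but nothing says so. Because the comparison is descriptive, the consequence is limited to how the interval in Table 15.2.1.8 is read.

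**What to change.** In booster SAP 4.1:

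1. State the null in one direction, matching the main-minus-booster difference in 4.5.7: post-primary exceeds post-booster by 0.08 log10 or more.
2. Replace 0.168 with a within-subject SD of log10 PRNT A differences from Groups 1 and 3 of the main trial, which section 2.2.2 says is already unblinded (for example V2 versus FU2, or V2 versus V4). Label it a proxy: in these groups the second injection is placebo, so both titers follow the same single active dose, not two active vaccinations a year apart.
3. Restate the power with that SD, or replace >80% by the ratio that can be excluded with 80% power over a range of correlations, as in the table above (1.19-fold at 0.875 to 1.42-fold at 0.50).

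The cost is one paragraph and one SD from existing data. Enrolment, analyses and tables are unchanged. The price is that the stated power will probably look less favourable.
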